4.6 Benefit/Risk Assessment

The safety and efficacy of avacincaptad pegol were demonstrated in two pivotal randomized, multi-center, double-masked, sham-controlled, 18- and 24-month studies (OPH2003 [GATHER1] and ISEE2008 [GATHER2], respectively) in patients with GA secondary to AMD. A total of 733 patients were treated in these studies. Patient ages ranged from 51 to 97 years with a mean of 77 years. In total 26, 292, and 83 patients were treated with avacincaptad pegol 1 mg, 2 mg, and 4 mg respectively, and 332 patients received sham.

The most frequently reported Treatment Emergent Adverse Events (TEAEs) in those participants receiving avacincaptad pegol 2 mg in the pivotal clinical studies OPH2003 and ISEE2008 were related to injection procedure. The most common adverse reactions ($\geq 5\%$ and greater than sham) reported up to 12 months were conjunctival hemorrhage (13%), increased IOP (9%), and Choroidal Neovascularization (CNV; 7%).

Both Study OPH2003 and Study ISEE2008 demonstrated robust statistical superiority of avacincaptad pegol over sham, through a substantial reduction in GA lesion growth, after one year of treatment. In both pivotal studies, avacincaptad pegol was shown to elicit a treatment effect by Month 6 that was persistent and continued to increase over time as measured by the absolute difference of GA growth between intervention groups.

The consistent safety and efficacy results from two independent, randomized, adequately well-controlled studies in patients with GA secondary to AMD support a favorable benefit/risk profile of avacincaptad pegol 2 mg for treatment in patients with GA secondary to AMD, a serious progressive disease that leads to irreversible blindness, especially in an increased aging population with limited, or no effective and safe treatment options available.

More detailed information about the known and expected benefits and risks and reasonably expected adverse events (AEs) of avacincaptad pegol can be found in the IB.

Adherence to eligibility criteria and study assessments may minimize potential risks to study participants. The safety of study participants will be monitored by the sponsor through remote data review and will be facilitated by timely entry of clinical data into the electronic data capture system (EDC) and reporting of serious adverse events (SAEs) by the investigator during study conduct.

5 TRIAL OBJECTIVES

5.1 Objectives

The objectives of this trial are to assess long-term safety of avacincaptad pegol monthly intravitreal administration for patients with GA who completed Study ISEE2008 (GATHER2) through the Month 24 visit on study treatment (either avacincaptad pegol or Sham).

5.2 Endpoints

Primary Endpoint:

- AEs

Secondary Endpoints:

- Immunogenicity
- Pharmacokinetics

Exploratory Endpoints:

- Ophthalmic variables
 - best corrected visual acuity (BCVA)
 - low luminance visual acuity (LLVA)
 - intraocular pressure (IOP)
 - ophthalmic examination

6 TRIAL DESIGN

This is an open-label, multicenter, 18-month extension study. Approximately 280 patients who completed Study ISEE2008 (GATHER2) through the Month 24 visit on study treatment (either avacincaptad pegol or Sham) will be administered avacincaptad pegol 2 mg monthly from Month 1 through Month 17. All patients, regardless of treatment received in ISEE2008 (avacincaptad pegol or Sham), will receive avacincaptad pegol 2 mg monthly.

All patients will have a final follow up visit at Month 18 or if the study is terminated early, Month 18 final follow up procedures will be followed. The end of the study is defined as the date of the last study assessment (See [Section 3](#)) for the last subject in the study globally.

Premature termination of this clinical trial may occur because of a regulatory authority decision, change in opinion of the Institutional Review Board (IRB)/Ethics Committee (EC), or at the discretion of Astellas.

7 PROCEDURES

7.1 Refraction, Visual Acuity, and Low Luminance Visual Acuity

Refraction, Vision Testing, and Low Luminance Vision Testing will be performed at all time-points specified in [Section 10.2](#) “Trial Assessments”. BCVA is also required at any other time-point in the event of an ocular AE in the study eye. Retro-illuminated modified Ferris-Bailey Early Treatment Diabetic Retinopathy Study (ETDRS) charts are used starting at 4 meters (see [Appendix 17.1](#)).

When refraction and ETDRS BCVA measurements are required by the trial protocol, these will be performed only by certified VA examiners with access to the previous VA measurement and the previous protocol refraction.

All necessary materials and instructions for these assessments will be provided by Astellas.

These assessments should always be performed in the following order: Refraction, ETDRS BCVA, and Low Luminance Visual Acuity.

7.2 Tonometry

Tonometry will be performed at all time-points specified in [Section 10.2](#) “Trial Assessments”. The IOP should be measured and recorded pre-injection and at least 30 minutes after the injection and IOP must be < 30 mmHg before the subject leaves the clinic. For the post-injection tonometry, proper care should be taken to minimize the risk of contamination.

Goldmann applanation tonometry must be performed at Month 12 and Month 18/End of Study (EOS) or Early Withdrawal (EW), pre- and post-injection (as applicable). Tono-Pen may be used at all other timepoints. Goldmann applanation tonometry must also be used to verify IOP reading of ≥ 30 mmHg occurring at any time.

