3 STUDY ASSESSMENTS

Assessments	M1 ^a	M2	M3	M4	M5	M6	M7	M8	M9	M10	M11	M12	M13	M14	M15	M16	M17	M18/EOS (EW)
Informed Consent	X ^b																	
Refraction and ETDRS BCVA ^{c,k}	X	X	X	X	X	X	X	X	X	X	X	X	X	X	X	X	X	X
LLVA ^c	X					X						X						X
Tonometry ^{c,d,e} /Ophthalmologic Examination ^{c,f}	X	X	X	X	X	X	X	X	X	X	X	X	X	X	X	X	X	X
Color Fundus Photography ^c	X					X						X						X
Fluorescein Angiography ^c												X						X
Optical Coherence Tomography ^c	X	X	X	X	X	X	X	X	X	X	X	X	X	X	X	X	X	X
Fundus Autofluorescence ^c	X					X						X						X
Urine Pregnancy (If Applicable) ^g	X	X	X	X	X	X	X	X	X	X	X	X	X	X	X	X	X	X
Immunogenicity Sampling ^h	X ⁱ	X		X			X						X					X
PK Sampling ^h	X ⁱ	X		X			X						X					X
Avacincaptad pegol 2 mg Administration	X	X	X	X	X	X	X	X	X	X	X	X	X	X	X	X	X	
Concomitant Medications	X	X	X	X	X	X	X	X	X	X	X	X	X	X	X	X	X	X
Adverse Events ^j	X	X	X	X	X	X	X	X	X	X	X	X	X	X	X	X	X	X

BCVA = best corrected visual acuity; EOS = end of study; ETDRS = Early Treatment Diabetic Retinopathy Study; EW = early withdrawal; IOP = intraocular pressure; LLVA = low luminance visual acuity; M = month; OLE = open-label extension; OU = both eyes; PK = pharmacokinetic; SE = study eye.

Refer to [Section 10.2 Trial Assessments](#) for additional details on assessments.

^aEnrollment into this OLE trial must be within 90 days of the patient's Month 24 visit in Study ISEE2008.

^bInformed consent must be signed before any other assessments are performed at Month 1 in this OLE trial.

^cOcular assessments are to be performed on both eyes (OU) pre-injection (as applicable) at Month 12 and Month 18/EOS (EW). Ocular assessments at all other trial visits are performed only on the study eye (SE). Refer to [Appendix 17.1](#) for details on procedures for refraction and vision testing.

^dGoldmann applanation tonometry must be performed at Month 12 and Month 18/EOS (EW), pre- and post-injection (as applicable). The Tono-Pen may be used at other times; however, Goldmann applanation tonometry must also be used to verify intraocular pressure (IOP) reading of ≥ 30 mmHg occurring at any time.

^eTonometry should be measured prior to the injection and at least 30 minutes after the injection as per [Section 10](#), Trial Conduct.

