 - BCVA (4 meters) using ETDRS chart (SE)
 - Tonometry (SE)
 - Full ophthalmologic examination (SE)
 - Optical coherence tomography (SE)
 - Treatment with IVT avacincaptad pegol 2 mg
- **Post-injection:**
 - Ophthalmic exam (SE) and Tonometry (SE): Following same procedures as outlined at Month 1.

Month 11 (±7 days)

- **Pre-Injection:**
 - Urine pregnancy test (if applicable)
 - Refraction
 - BCVA (4 meters) using ETDRS chart (SE)
 - Tonometry (SE)
 - Full ophthalmologic examination (SE)
 - Optical coherence tomography (SE)
 - Treatment with IVT avacincaptad pegol 2 mg
- **Post-injection:**
 - Ophthalmic exam (SE) and Tonometry (SE): Following same procedures as outlined at Month 1.

Month 12 (±7 days)

- **Pre-Injection:**
 - Urine pregnancy test (if applicable)
 - Refraction
 - BCVA (4 meters) using ETDRS chart (SE)
 - LLVA
 - Goldmann applanation tonometry and full ophthalmologic examination (OU)
 - Color fundus photography (OU)
 - Fluorescein angiography (OU, transit SE)
 - Optical coherence tomography (OU)
 - Fundus autofluorescence (OU)
 - Treatment with IVT avacincaptad pegol 2 mg
- **Post-injection:**
 - Ophthalmic exam (SE) and Tonometry (SE): Following same procedures as outlined at Month 1 (Note: Goldmann applanation tonometer must be used).

Month 13 (±7 days)

- **Pre-Injection:**
 - Urine pregnancy test (if applicable)
 - Immunogenicity and PK sampling
 - Refraction

- BCVA (4 meters) using ETDRS chart (SE)
- Tonometry (SE)
- Full ophthalmologic examination (SE)
- Optical coherence tomography (SE)
- Treatment with IVT avacincaptad pegol 2 mg
- **Post-injection:**
 - Ophthalmic exam (SE) and Tonometry (SE): Following same procedures as outlined at Month 1.

Month 14 (±7 days)

- **Pre-Injection:**
 - Urine pregnancy test (if applicable)
 - Refraction
 - BCVA (4 meters) using ETDRS chart (SE)
 - Tonometry (SE)
 - Full ophthalmologic examination (SE)
 - Optical coherence tomography (SE)
 - Treatment with IVT avacincaptad pegol 2 mg
- **Post-injection:**
 - Ophthalmic exam (SE) and Tonometry (SE): Following same procedures as outlined at Month 1.

Month 15 (±7 days)

- **Pre-Injection:**
 - Urine pregnancy test (if applicable)
 - Refraction
 - BCVA (4 meters) using ETDRS chart (SE)
 - Tonometry (SE)
 - Full ophthalmologic examination (SE)
 - Optical coherence tomography (SE)
 - Treatment with IVT avacincaptad pegol 2 mg
- **Post-injection:**
 - Ophthalmic exam (SE) and Tonometry (SE): Following same procedures as outlined at Month 1.

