Month 16 (±7 days)

- **Pre-Injection:**

- Urine pregnancy test (if applicable)
- Refraction
- BCVA (4 meters) using ETDRS chart (SE)
- Tonometry (SE)
- Full ophthalmologic examination (SE)
- Optical coherence tomography (SE)
- Treatment with IVT avacincaptad pegol 2 mg

- **Post-injection:**

- Ophthalmic exam (SE) and Tonometry (SE): Following same procedures as outlined at Month 1.

Month 17 (±7 days)

- **Pre-Injection:**

- Urine pregnancy test (if applicable)
- Refraction
- BCVA (4 meters) using ETDRS chart (SE)
- Tonometry (SE)
- Full ophthalmologic examination (SE)
- Optical coherence tomography (SE)
- Treatment with IVT avacincaptad pegol 2 mg

- **Post-injection:**

- Ophthalmic exam (SE) and Tonometry (SE): Following same procedures as outlined at Month 1.

Month 18/End of Study (Early Withdrawal)

- Urine pregnancy test (if applicable)
- Immunogenicity and PK sampling
- Refraction

- BCVA (4 meters) using ETDRS chart (OU)
- LLVA
- Goldmann applanation tonometry (OU)
- Full ophthalmologic examination (OU)
- Color fundus photography (OU)
- Fluorescein angiography (OU, transit SE)
- Optical coherence tomography (OU)
- Fundus autofluorescence (OU)

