4.5 Exploratory Endpoint(s) Analysis

The exploratory endpoints are ophthalmic findings. All the assessments will be mapped to a scheduled visit. The mapping rule is provided in Table 2 for BCVA, OE and IOP and Table 3 for LLVA.

Best Corrected Visual Acuity (BCVA)

The score and the change from baseline of BCVA (ETDRS letters) at each analysis visit will be summarized descriptively by cohort for the FAS.

Low Luminance Visual Acuity (LLVA)

The score and the change from baseline of LLVA (ETDRS letters) at each analysis visit will be summarized descriptively by cohort for the FAS.

Low Luminance Deficits (LLD)

The score and the change from baseline of LLD (ETDRS letters) at each analysis visit will be summarized descriptively by cohort for the FAS, where LLD is calculated by the difference of BCVA and LLVA at a same visit.

Intraocular Pressure (IOP)

Baseline IOP is the pre-injection IOP value before the first study drug administration in this study.

Pre-injection IOP is defined as the last IOP value before an injection on a visit with injection (whether ACP or other treatment) or the last IOP value on a visit without an injection.

Post-injection IOP is defined as the IOP value after one injection that is closest in time to the protocol-specified post-injection timepoint (but at least 30 minutes post-injection).

Pre-injection and post-injection IOPs at each analysis visit will be summarized descriptively by cohort for the SAF with in one table. The number and percentage of participants in categories of pre-injection IOP value (≤ 21 mmHg, 22-29 mmHg, 30-34 mmHg, ≥ 35 mmHg) will be summarized at each analysis visit for each cohort.

The change from baseline of pre-injection IOPs will be summarized at each analysis visit for each cohort.

Change of IOP at each analysis visit is the difference between the post-injection and pre-injection IOPs. Change of IOP at each analysis visit will also be summarized descriptively for each cohort. The number and percentage of participants in categories of change of IOP (≤ 0 mmHg, 1-5 mmHg, 6-10 mmHg, >10 mmHg) will be summarized at each analysis visit for each cohort.

The number and percentage of participants who experienced the following events will be summarized for each cohort. The events are:

- Either pre-injection or post-injection IOP ≥ 35 mmHg,
- Had a paracentesis and
- Received IOP-lowering medications.

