4.10 Additional Conventions

4.10.1 Analysis Windows

Study Day for analysis windows will be calculated as: Date of visit/assessment – first dose of study drug in this study + 1.

The assignment of analysis visit will be consistent across all by-visit analysis datasets, and will follow the respective step-by-step algorithm:

- All assessment visits will be windowed, per the below tables, regardless of SE/FE, scheduled/unscheduled status, injection date, or pre/post-injection status.
- Baseline derivations will follow the definitions as stated in Section 4.1.

An analysis flag will be created for each record by following rules.

- **General Rules for Analysis Flags**
 - Scheduled visits falling into their respective analysis window will be prioritized over unscheduled visits.
 - If multiple observations still exist, the observation closest to the scheduled day will be selected for the analysis visit.
 - If there are two observations that have the same distance from the scheduled day, the value that is after the scheduled day will be selected for the analysis visit.
 - If more than one observation (excluding OE/IOP observation) is made on the same day, an average value for continuous measurement, or the worst value for categorical measurement, will be used for the analysis visit.
 - Any additional rules will be prespecified and documented in the TLF specifications.
- **Additional Rules for OE/IOP Analysis Flags except those in the Analysis Visit Month 18**
 - The OE/IOP records on a visit falling into its respective analysis window and with at least one SE ACP pre-injection and one SE ACP post-injection records will be firstly selected.
 - If there are no OE/IOP records satisfying the first rule, the records on a visit (whether scheduled or unscheduled) and with at least one SE ACP pre-injection and on SE ACP post-injection records will be selected.
 - If there is no OE/IOP records satisfying the above two rules, the records will be selected from a visit day (whether scheduled or unscheduled) that contain at least one pre-injection or one post-injection record to separately summarize the pre-injection and post-injection IOPs.
 - The closest OE/IOP observation to the target time will be selected for analysis.
 - If both Tonopen and Goldmann measurement are recorded available at the same time per CRF, the Goldmann measurement will be prioritized.

Listings will include all scheduled, unscheduled, and early withdrawal data.

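### Goldmann tonometry is mandatory at Months 12 and 18 but not at the Month 1 baseline, so IOP change from baseline at those visits can include a change of instrument

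*Protocol*

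**What the plan says.** **Instrument by visit.** Protocol 7.2 states: "Goldmann applanation tonometry must be performed at Month 12 and Month 18/End of Study (EOS) or Early Withdrawal (EW), pre- and post-injection (as applicable". For the remaining visits it adds: "Tono-Pen may be used at all other timepoints". Footnote d of the schedule in Protocol 3 repeats the permission: "The Tono-Pen may be used at other times". The visit lists in Protocol 10.2 agree. Month 1 lists study-eye tonometry with no instrument named, while Months 12 and 18 both name Goldmann. Any reading of 30 mmHg or more must be verified by Goldmann at any visit.

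**Baseline and change.** SAP 4.5 defines the reference value: "Baseline IOP is the pre-injection IOP value before the first study drug administration in this study". It sets no condition on instrument. It continues: "The change from baseline of pre-injection IOPs will be summarized at each analysis visit for each cohort". The mean of that change is also plotted over time. A visit without an injection contributes its last IOP value as the pre-injection value, which is how Month 18 enters.

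**Instrument in the analysis.** The only SAP rule on the device is a tie-break in 4.10.1: "If both Tonopen and Goldmann measurement are recorded available at the same time per CRF, the Goldmann measurement will be prioritized". The SAP has no analysis of IOP by instrument, whether matched, stratified or as a sensitivity summary.

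**The concern.** The plan fixes the instrument at the end of the comparison and leaves it open at the start. If a site used a Tono-Pen at Month 1, the changes at Month 12 and Month 18 subtract a reading on one device from a reading on another. A systematic difference between the devices would then appear as a change in IOP.

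The plan does not treat the two devices as interchangeable. Goldmann verifies high readings, is compulsory at two visits, and is preferred when both are recorded.

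Nothing in the design removes an offset. Every participant receives the drug, so there is no untreated group. The fellow eye cannot serve as a reference because its ocular assessments are scheduled only at Month 12 and Month 18/EOS (EW), so it has no scheduled Month 1 reading.

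The trial's purpose is long-term safety, and Protocol 4.6 lists increased IOP among the most common adverse reactions (9% up to 12 months, greater than sham). A reader of the IOP tables will look at these changes.

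**Working it through.** The plan gives no figure to reproduce. The sample size of about 280 reflects the parent-study completers expected to enrol, and no IOP standard deviation or margin is stated.

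**1. Which comparisons are affected**

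- Month 1: Tono-Pen or Goldmann (Protocol 3, 7.2, 10.2).
- Months 2-11 and 13-17: Tono-Pen or Goldmann, with Goldmann verification at 30 mmHg or more.
- Months 12 and 18/EOS (EW): Goldmann.
- Early-withdrawal readings are assigned to analysis visits by study day (SAP 4.10.1, Table 2). The IOP selection rules prefer a visit with both pre- and post-injection records but accept an unpaired one. A Goldmann early-withdrawal reading can therefore enter a visit other than Month 12 or 18.
- The Month 12 post- minus pre-injection change is unaffected, because both readings are Goldmann.

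**2. Size of the distortion**

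Let p be the share of baselines taken by Tono-Pen and b the mean Tono-Pen minus Goldmann difference. The spurious mean change at a Goldmann visit is −p × b. Neither input is in the documents, so the values below are assumptions. The table gives the absolute size in mmHg; the sign is opposite to that of b.

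| b (mmHg) | p = 0 | p = 50% | p = 100% |
|---|---|---|---|
| 0 | 0 | 0 | 0 |
| 0.5 | 0 | 0.25 | 0.5 |
| 1 | 0 | 0.5 | 1 |
| 2 | 0 | 1 | 2 |
| 3 | 0 | 1.5 | 3 |

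**3. Against sampling error**

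The 95% half-width of a mean change is 1.96 × SD/√n. With an assumed SD of change of 2.5 to 4 mmHg:

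- n = 280: 1.96 × 2.5/√280 = 0.29 to 1.96 × 4/√280 = 0.47 mmHg.
- n = 70: 1.96 × 2.5/√70 = 0.59 to 1.96 × 4/√70 = 0.94 mmHg.

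The illustrative 0.5 mmHg would just exceed sampling error for the total group but not for a cohort of 70. It would not shrink with more participants.

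**4. Between cohorts**

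A contrast between cohorts is distorted only by the difference in their Tono-Pen shares. For an assumed difference of 10 to 20 points and b of 0.5 to 3 mmHg, this is 0.1 × 0.5 = 0.05 to 0.2 × 3 = 0.6 mmHg.

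**5. What matching would leave**

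Same-instrument pairs at Months 12 and 18 are at most 280 × (1 − p): 140 at p = 50% and 0 at p = 100%, before dropout.

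**The case against.** **IOP is exploratory, with no hypothesis and no inference.** This stands and limits the weight of the point. No test, sample size or primary analysis changes.

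**IOP harm is captured elsewhere.** This also stands. The AE analyses include the increased-IOP preferred term, two AESI categories concern IOP, and SAP 4.5 counts IOP of 35 mmHg or more, paracentesis and IOP-lowering medication. None of these uses change from baseline.

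**A reader might infer that most participants have a Tono-Pen baseline and that the mean change is therefore biased.** The documents do not support this. The Tono-Pen is permitted, not required; sites need Goldmann in any case; and neither the size nor the direction of a device difference is given. Zero is within the possible range.

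**A reader might infer that a sustained rise would be hidden.** This goes too far. The SAP reports every visit, not only Months 12 and 18. Where a site kept to the Tono-Pen, Months 2-11 and 13-17 share the baseline instrument and would show such a rise. A pure device step would tend to appear at Month 12 and reverse at Month 13. That pattern can be recognised only if the output shows where the instrument changed, and the planned output does not.

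**Without a control, change from baseline would not isolate a drug effect even with one tonometer.** True. The instrument switch is a separate source of error, and an avoidable one.

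**It is too late to change Month 1.** Largely true. Enrolment must fall within 90 days of the parent study's Month 24 visit, and the parent study report was final on 06 Dec 2023. Ninety days from even that date ends on 5 March 2024, a week after Amendment 01 (27 February 2024). The useful remedy is therefore in the SAP.

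**Conclusion.** The point holds as a gap in the measurement and analysis plan. For any participant with a Tono-Pen baseline, the Month 12, Month 18 and early-withdrawal changes from baseline in pre-injection IOP combine a possible instrument difference with real change, and the planned output does not separate them.

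The mismatch follows directly from the text. Its numerical effect does not: 0.5 mmHg is an illustration resting on an assumed 50% share and 1 mmHg difference, and the effect is 0 if all sites used Goldmann at Month 1 or the devices agree. The consequence is a risk of misreading one exploratory table and one plot. The documents do not show that the trial's safety conclusion is compromised. The change is still worth making, because it is cheap and prevents that misreading.

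**What to change.** **SAP 4.5**

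- Keep the planned all-participant summary of change from baseline.
- Add the same summary by tonometer pair (same versus mixed instrument) at every analysis visit, including early-withdrawal readings placed by the windows.
- Report the number of participants by instrument at Month 1. This replaces the assumed share with the actual one.
- Mark Months 12 and 18 on the mean-change plot as visits with mandatory Goldmann.
- State that matched-pair numbers at Months 12 and 18 may be much smaller than the total, since only participants with a Goldmann baseline contribute. State also that Months 2-11 and 13-17 carry the same-instrument trend for those with a Tono-Pen baseline, so far as the Tono-Pen was used again.

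The tie-break in SAP 4.10.1 implies that the CRF records the instrument, so this costs SAP wording and one more classification variable, with no new data.

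**Protocol 3 (footnote d), 7.2 and 10.2**

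For any participant not yet past Month 1, and in future studies, require Goldmann for the Month 1 pre-injection study-eye reading. It replaces a reading rather than adding one, and sites already need the instrument. With p = 0 the instrument component at Months 12 and 18 is 0 for any device difference. In this trial it would probably reach few participants or none.
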